The effect of AposTherapy on pain and function in Knee Osteoarthritis population.

A randomized controlled trial

Clinical Study Protocol

Study Type: Randomized controlled trial

PI

[name], MPH

Professor and Chairman of Rehabilitation Medicine

Albert Einstein College of Medicine

Chairman, Department of Rehabilitation Medicine

Montefiore Medical Center

Protocol Version and Date: Version 1.6, 12.20.2016

Study Synopsis	
Title of the study	The effect of AposTherapy on pain and function in Knee Osteoarthritis (OA) population. A randomized controlled trial
Study objective	To evaluate the effect of AposTherapy on pain and function in knee OA population.
Outcome measures	
Primary outcome measures:
 
 • Pain and function at 1-year post treatment initiation 
Secondary outcome measure:
 
 • Total healthcare utilization and costs of physical therapy and AposTherapy will be assessed, including physical therapy, ED visits, pharmacological pain treatments, injections, imaging studies, surgical procedures, physician visits related to knee pain and total physician visits • PROMIS Pain Interference and Physical Function • Pain medication consumption • Quality of life • Gait assessment • 6-min walk test • Blood pressure and resting heart rate • Adherence to treatment - AposTherapy (Patient to have step counter permanently attached to AposTherapy device, downloaded at each visit • Overall activity and sleep patterns, both groups. Will be measured via FitBit Charge HR

	
(http://www.fitbit.com/chargehr#i.f9n1ye1ehxd30p) motion sensor worn for one week after each evaluation session, mailed back via prepaid mailer at the end of the week.

Study design	A randomized controlled trial (AposTherapy compared to traditional physical therapy)
STUDY POPULATION	Patients suitable for inclusion in this study will be those fulfilling the following:
Inclusion criteria	
 • Patients suffering from symptomatic knee OA (uni/bilateral) for at least six months, fulfilling the ACR clinical criteria for OA of the knee, and having radiographically assessed OA of the knee according to the Kellgren and Lawrence scale. • Patients with VAS pain score of ≥ 3cm (measured at baseline). • Males and females between the ages of 40-75. • $17 < \text{BMI} < 40$ • Ambulatory and active patients that can participate in a rehabilitation program that includes daily walking • Stable medical regimen (no recent changes to their pain medication within a month) • Able to walk at least 50 meters • Able to understand, read and sign the informed consent form • English or Spanish speaking
Exclusion Criteria	Patients with any of the following are to be excluded from the study:

- Patients suffering from acute septic arthritis.
- Patients suffering from inflammatory joint disease such as rheumatoid arthritis.
- Patients who received a viscosupplementation /corticosteroid injection within 3 months of the study
- Patients with diagnosis of avascular necrosis of the knee.
- Patients with diagnosis of neuromuscular disease.
- Patients with more than 3 falls in the last 12 months, OR any fall with an injury in the last 12 months.
- Patients exhibiting a lack of physical or mental ability to perform or comply with the study procedure.
- Patients with a history of pathological osteoporotic fracture
- Patients with referred pain in the knees from back or hip joint symptoms.
- Patients with severe back pain, ≥ 4 cm in visual analogue scale or radiating leg pain
- Patients with generalized body pain (both upper and lower extremities, such as fibromyalgia)
- No major surgery to the affected limb and contralateral limb (e.g. no joint replacements or surgical fracture repair)
- No major cardiovascular comorbidities (able to enroll in an active exercise program)
- Patient started on lipid lowering medication in last 3 months
- Any change in blood pressure medications
- No recent physical therapy (no more recent than 6

	
months) on the affected limb
 
 • No active heart disease (ischemia or heart failure admissions within 6 months) and no active COPD (exacerbation within 6 months) • No active malignancies on ongoing treatment • Patient with neurological gait pattern [2] • Patient requiring assistive device during gait analysis.
Total number of patients	
One-hundred and forty-seven (147) individuals will be randomly assigned to one of two groups; traditional physical therapy or AposTherapy on a 1:2 ratio (49:98).
 
A sample size of 147 will yield 80% power to detect an expected difference on the WOMAC pain scale, with components measured on VAS scales from 0 to 10 and a summary score standardized to also range from 0 to 10, of 1.5 at a 2-sided alpha of 0.05. The difference corresponds to a clinically meaningful moderate effect size of 0.4 standard deviation units assuming a typical standard deviation of 2.65. Anticipating an attrition rate of 10%, we aim at recruiting 162 patients for the trial.

Study groups	
Patients will be randomly assigned to one of the following groups:
 
 • Patients with knee OA treated with AposTherapy • Patients with knee OA treated with traditional physical therapy
Assessment time points	
Patients will be enrolled in the study and have clinical evaluations at the following time points:
 
 • Pre-treatment • 4 weeks following treatment initiation

- 8 weeks following treatment initiation
- 12 weeks following treatment initiation
- 24 weeks following treatment initiation
- 52 weeks following treatment initiation

**The effect of AposTherapy on pain and function in Knee Osteoarthritis (OA) population. A
randomized controlled trial**

1. Background

AposTherapy is a home-based exercise program utilizing footwear that causes exercise with normal daily activity that may significantly improve function in patients with knee pain in general, and specifically knee osteoarthritis (OA). Capitalizing on the reported excellent adherence and clinical benefit of Apos Therapy in patients with significant lower limb arthritis, we propose to evaluate this as a conservative treatment that may supplant/supplement traditional pain medications and physical therapy in knee OA population. [3-6]

A potential use of AposTherapy as a replacement for traditional physical therapy may yield a less costly, more effective therapy with better adherence. Problems with traditional therapy include poor patient adherence (patients often do not complete the sessions and have very poor adherence (about 50-60%) to home therapy programs [7]), added cost of travel (which may be more than \$100 per session for ambulette or access-a-ride for eligible patients), and the lack of continuation in an ongoing exercise program, leading to relapse and need for retreatment. Additionally, access to physical therapy is limited for many patients since there are not enough available outpatient therapy services to meet the needs of all patients. Finding an alternative exercise program that will increase adherence, decrease total therapy visits, and improve patient's outcomes with decreased dependence on pain medications is a high priority from both patient care and cost management perspectives.

AposTherapy potentially overcomes many of these issues with improving/modifying abnormal biomechanics (therefore decreasing pain), and a home-based exercise program utilizing footwear that causes exercise with normal activity by promoting perturbation. This biomechanical approach may significantly reduce pain and improve function in patients with

knee OA. Capitalizing on the reported excellent adherence and clinical benefit of AposTherapy in patients with significant knee OA, we propose to evaluate the biomechanical exercise (wearing an appropriately calibrated shoe at home for a prescribed amount of time each day) as a conservative treatment that may supplement or supplant traditional pain medications, interventional pain procedures and physical therapy in an at-risk urban inner city population with knee OA.

2. Study objective

The purpose of the current study is to evaluate the effect of this home-based biomechanical device and treatment (AposTherapy) in knee OA population. This will be a randomized single blinded (evaluator) trial of conventional physical therapy versus AposTherapy in patients with knee OA treated for one year.

In order to assess the efficacy of the intervention with AposTherapy on our patient population, a set of primary and secondary outcome measures will be defined:

3. Outcome measures

3.1. Primary outcome measures:

- Pain and function at 1 year following treatment initiation

3.2. Secondary outcome measure:

- Total healthcare utilization and costs of physical therapy and AposTherapy will be assessed, including physical therapy, ED visits, pharmacological pain treatments, joint injections, imaging studies, surgical procedures, physician visits related to knee pain and total physician visits
- Pain medication consumption
- Quality of life
- Gait assessment
- 6-min walk test

- Blood pressure and resting heart rate
- Adherence to treatment - AposTherapy group (Patient to have step counter permanently attached to AposTherapy device)
- Overall activity and sleep patterns, both groups. Will be measured via FitBit Charge HR (<http://www.fitbit.com/chargehr#i.f9n1ye1ehxd30p>) motion sensor worn for one week after each evaluation session, mailed back via prepaid mailer at the end of that week.

4. Materials and Methods

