4.6. Sample size

Our target recruitment is 147 individuals randomly assigned to one of two groups; traditional physical therapy or AposTherapy, on a 1:2 ratio. A sample size of 147 patients will yield 80% power to detect an expected difference on the WOMAC pain scale, with components measured on VAS scales from 0 to 10 and a summary score standardized to also range from 0 to 10, of 1.5 at a 2-sided alpha of 0.05. The difference corresponds to a

[figure not shown]
clinically meaningful moderate effect size of 0.4 standard deviation units assuming a typical standard deviation of 2.65. Anticipating an attrition rate of 10%, we aim at recruiting 162 patients for the trial (54 patients will be assigned to traditional physical therapy and 108 patients will be assigned to AposTherapy)

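### The synopsis and section 4.6 give two numbers to be randomised, 147 and 162; the 10% attrition inflation behind 162 is also slightly short, which matters much less

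*Combined protocol and SAP*

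**What the plan says.** Three places give the number of patients.

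- **Study Synopsis, Total number of patients.** Of 147 patients it says: "individuals will be randomly assigned to one of two groups; traditional physical therapy or AposTherapy on a 1:2 ratio (49:98"). Power is attached to the same figure: "A sample size of 147 will yield 80% power to detect an expected difference on the WOMAC pain scale". The cell ends: "Anticipating an attrition rate of 10%, we aim at recruiting 162 patients for the trial".
- **Section 4.6, Sample size.** It opens: "Our target recruitment is 147 individuals randomly assigned to one of two groups; traditional physical therapy or AposTherapy, on a 1:2 ratio". It closes by recruiting 162, split as follows: "54 patients will be assigned to traditional physical therapy and 108 patients will be assigned to AposTherapy".
- **Budget tables under Resources.** Transport and subject reimbursement are each costed at $100 for 147 patients. The step-counter and Fitbit lines cover 37 patients, described as a quarter of the patients; a quarter of 147 is 36.75, and a quarter of 162 would be 40.5.

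The primary outcomes are WOMAC pain and function at one year (sections 3.1 and 4.9), so the attrition that matters is loss by week 52. Nowhere do the documents say that 147 is the number of completers or evaluable patients.

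**The concern.** Section 4.6 contains two recruitment targets and two assigned totals. For 147 the words are that patients are randomly assigned; for 162 they are that patients are recruited and assigned to arms. In a two-arm randomised trial these mean the same thing.

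The attrition sentence makes sense only if 147 is the number wanted after losses and 162 the number entered. The text instead calls 147 the number entered, and the budget is built on it. Someone working from the opening sentences or the costing could close randomisation 15 patients early, with no allowance for withdrawal. A later reader could not tell whether a trial of 147 had met its target or fallen short.

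A smaller question is whether 162 delivers 147 after the stated loss.

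**Working it through.** **Inputs.** From the synopsis and section 4.6: base number 147 (49:98), attrition 10%, inflated number 162 (54:108), two-sided alpha 0.05, difference 1.5 points, SD 2.65, stated effect size 0.4 SD.

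**Step 1: reproduce 162.** Multiplying up gives 147 × (1 + 0.10) = 161.7, which rounds to 162, the plan's figure. Since a fraction 0.10 of those entered is lost, the correct form is N = n / (1 − 0.10) = 147 / 0.9 = 163.3. That is 164, or 165 (55:110) to keep an exact 1:2 split.

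**Step 2: expected number at week 52 with 10% loss.**

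| Randomised | Expected at week 52 | Against 147 |
|---|---|---|
| 147 (49:98) | 147 × 0.9 = 132.3 | −14.7 |
| 162 (54:108) | 162 × 0.9 = 145.8 (48.6:97.2) | −1.2 |
| 165 (55:110) | 165 × 0.9 = 148.5 | +1.5 |

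The two readings of the plan differ by 145.8 − 132.3 = 13.5 patients at the primary time point.

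**Step 3: what this does to power.** I used a two-sample t test with noncentral t, two-sided 0.05 and 1:2 allocation. The noncentrality is d / √(1/n₁ + 1/n₂), with n₁ = N/3 and n₂ = 2N/3, which equals d / √(4.5/N). The plan's inputs give two values of d: 1.5 / 2.65 = 0.566, and the stated 0.4. Both are shown.

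| N at week 52 | Power, d = 0.566 | Power, d = 0.4 |
|---|---|---|
| 147 | 89.5% | 62.2% |
| 145.8 | 89.3% | 61.9% |
| 132.3 | 86.1% | about 58% |

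Using 162 where about 164 was needed costs about 0.2 points at d = 0.566 and under 0.4 points at d = 0.4. Ending at 147 when 162 was meant costs 89.3 − 86.1 = 3.2 points at d = 0.566 and about 4 points at d = 0.4.

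**Step 4: is 147 itself a required number?** By the normal approximation, N = 4.5 × ((1.960 + 0.842) / d)². At d = 0.566 this is 110.2, so 111 in whole patients at 1:2. At d = 0.4 it is 220.7, so 222. Neither stated effect gives 147 at 80% power.

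**The case against.** The best answer is that the intended meaning can be recovered. In both places 147 is tied to the power statement, the attrition sentence then raises the number to 162, and section 4.6 ends with an explicit 54:108 split. The budget is a costing table and not a randomisation rule. It also disagrees with section 8 on payments: $100 per patient, against $40 at each of six assessments plus $95, or 6 × 40 + 95 = $335. It cannot decide between 147 and 162.

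Most of this stands, and it is why 162 is the figure to keep. It does not remove the contradiction, because the completer reading of 147 is only implied while the opposite is written in both places.

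The second objection is that the inflation slip is trivial, and that is right. An attrition guess of 10% is not accurate to one patient, and a shortfall of 1.2 changes nothing of substance.

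Two stronger readings are tempting, and the documents support neither.

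- **That the withdrawal allowance fails and leaves the trial underpowered.** At 162 randomised it delivers 99% of 147 (145.8 / 147). At 1.5 points and SD 2.65, power stays above 80% even at 132.3 patients. At 0.4 SD it is well below 80%, but it is so at 147 too; the cause is the effect size, not attrition.
- **That the trial will stop at 147.** Nothing says so. The risk lies in the wording.

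**Conclusion.** The point holds as an inconsistency in a sample size the trial relies on. The synopsis and section 4.6 give both 147 and 162 as numbers assigned, and the budget follows 147. Taken literally, 147 leaves about 132 patients at week 52; 162 leaves about 146. This conflict is the main error, worth 15 randomised patients and roughly 3 to 4 points of power.

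The inflation by 1.1 in place of division by 0.9 is a genuine but minor slip: 1.2 expected patients at week 52.

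The week-52 figures assume that the plan's 10% applies equally in both arms. The power figures assume an unadjusted two-sample comparison of WOMAC pain at the plan's own inputs. Those inputs are not consistent with each other: the plan describes 1.5 points as an "effect size of 0.4 standard deviation units assuming a typical standard deviation of 2.65", whereas 1.5 / 2.65 = 0.566. That is a separate defect, but it means 147 should not be presented as the number needed for 80% power.

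**What to change.** 1. In the synopsis, section 4.6 and the budget, state one figure: 162 randomised (54:108), with about 146 (48.6:97.2) expected at week 52 after 10% loss.
2. Stop describing 147 as the number randomly assigned or as the target recruitment. Describe it only as the calculation figure before attrition.
3. Restate power at about 146 from one consistent effect size and SD. It is about 89% for 1.5 points with SD 2.65, or about 62% for 0.4 SD.

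No patients are needed beyond the 162 already planned, and moving to 164 or 165 is not worth insisting on.

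**Cost.** The stated number at week 52 becomes slightly less favourable, 146 in place of 147. Costing the other 15 patients adds 15 × ($100 transport + $100 reimbursement) = $3,000 at the budget's own rates. If the section 8 payments apply, the same 15 patients add 15 × ($100 + $335) = $6,525, so the two reimbursement figures should be reconciled in the same edit. The device lines set at a quarter of patients would also rise slightly.

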4.1. Trial Design

Single blinded (evaluator), single-center, randomized controlled trial.

4.2. Recruitment

Recruitment will be at the Montefiore Medical Center Moses Campus with therapy being provided on site.

4.3. Randomization

Blocked randomization will be used to assign to their respective treatment arm. The assigning ratio will be one to two; The random method of selection will be through a computerized random number generator. The on-site coordinator will be responsible for entering and maintaining the subject randomization information.

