4.5. Population

We will offer this option to patients at the general clinic sites, orthopedic clinics, and general medical and rehabilitation practices of the Montefiore Medical Group and Departments of Orthopedics and Rehabilitation Medicine Practices, who would normally be referred for physical therapy for their knee pain.

Inclusion Criteria:

- Patients suffering from symptomatic knee OA (uni/bi lateral) for at least six months, fulfilling the ACR clinical criteria for OA of the knee, and having radiographically assessed OA of the knee according to the Kellgren and Lawrence scale.
- Patients with VAS pain score of ≥ 3 cm (measured at baseline).
- Males and females between the ages of 40-75.
- $17 < \text{BMI} < 40$
- Ambulatory and active patients that can participate in a rehabilitation program that includes daily walking
- Stable medical regimen (no recent pain medication changes within a month)
- Able to walk at least 50 meters
- Able to understand, read and sign the informed consent form
- English or Spanish speaking

Exclusion Criteria:

- Patients suffering from acute septic arthritis.
- Patients suffering from inflammatory joint disease such as rheumatoid arthritis.
- Patients who received a viscosupplementation/corticosteroid injection within 3 months of the study.
- Patients with diagnosis of avascular necrosis of the knee.
- Patients with diagnosis of neuromuscular disease.

- Patients with more than 3 falls in the last 12 months, OR any fall with an injury in the last 12 months.
- Patients exhibiting a lack of physical or mental ability to perform or comply with the study procedure.
- Patients with a history of pathological osteoporotic fracture
- Patients with referred pain in the knees from back or hip joint symptoms.
- Patients with severe back pain, ≥ 4 cm in visual analogue scale or radiating leg pain
- Patients with generalized body pain (both upper and lower extremities, such as fibromyalgia)
- No major surgery to the affected limb and contralateral limb (e.g. no joint replacements or surgical fracture repair)
- No major cardiovascular comorbidities (able to enroll in an active exercise program)
- Patient started on lipid lowering medication in last 3 months
- Any change in blood pressure medications
- No recent physical therapy (no more recent than 6 months) on the affected limb
- No active heart disease (ischemia or heart failure admissions within 6 months) and no active COPD (exacerbation within 6 months)
- No active malignancies

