4.8. Assessment time points

Visits for evaluation will be done in a blinded fashion with independent evaluators who will perform all follow-up evaluations. Patients will have all outcome measures on initial entry into the study (pre-treatment), at 4 weeks, 8 weeks, 12 weeks, 24 weeks and 52 weeks after entry into the study.

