In- /Exclusion Criteria	X							
Radiography	X							
Randomization	X							
Administer traditional physical therapy		Physical Therapy is administered according to the protocol for the duration of enrollment in the study						
Administer Biomechanical Device		X						
Adjustment Biomechanical Device			X	X	X	X		
VAS and ODI		X	X	X	X	X	X	
Secondary outcome measures		X	X	X	X	X	X	
Adverse Events		X	X	X	X	X	X	

Resources

AposTherapy	Montefiore

 • Training for Montefiore PTs • Full-time Apos resource to manage program on-site at Montefiore • AposTherapy devices 	
 • Clinical Principle Investigator Lead • Research staff – 2 coordinators • Data informatics, including patient population, demographics, historical costs, etc. • Research infrastructure including IRB, recruitment, clinical expertise • Study materials • Step counter/Fitbit monitors

Staff	Salary - Rate/Hr	Fringe	FTE or Hours	Total Cost
Attending Physician Supervision	\$165,000	30.5%	0.2	\$43,065
Study coordinator	\$0	0.0%	2	\$0
These will be Everest individuals				
Informatics costs	\$75		100	\$7,500
Biostatistical support	\$150		100	\$15,000
CMO staff support	\$65,000	30.5%	0.5	\$42,413
Total Staffing Cost				\$107,978
Materials	Cost per Unit	# of Patients	Qty	Subject Costs
Step counters:				
25% of Patients and 10% loss	\$50	37	41	\$2,050
Fitbit HR Monitors:				
25% of Patients	\$150	37	41	\$6,150
Mailing to Recover step counter/Fitbit:*	\$10	37		\$14,800

Transportation costs:	\$100	147		\$14,700
Subject Complete Reimbursement	\$100	147		\$14,700
Zeno Walkway	\$20,000		1	\$20,000
Total Materials				\$72,400
Total cost of the study				\$180,378

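### Randomisation information sits with the on-site coordinator under blocked 1:2 allocation, with no stated concealment or release rule, and the schedule places randomisation before the baseline VAS that decides eligibility

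*Combined protocol and SAP*

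**What the plan says.** Section 4.3 states the method ("Blocked randomization will be used to assign to their respective treatment arm"), the ratio ("The assigning ratio will be one to two"), the source of the sequence ("The random method of selection will be through a computerized random number generator") and the custody arrangement ("The on-site coordinator will be responsible for entering and maintaining the subject randomization information"). It gives no block size and does not say whether the size varies or is withheld from site staff. Neither this section nor any other mentions a central or web system, sealed envelopes, a list holder independent of recruitment, or the point at which an assignment is released.

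Section 4.1 describes the trial as "Single blinded (evaluator), single-center, randomized controlled trial". Section 4.2 puts recruitment and therapy on one campus. Section 4.8 defines the blinding: "Visits for evaluation will be done in a blinded fashion with independent evaluators who will perform all follow-up evaluations".

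Section 4.5 lists as an inclusion criterion "Patients with VAS pain score of ≥ 3 cm (measured at baseline"). The study schedule marks consent, eligibility and randomisation in the screening column (week -2). VAS is first marked at week 0.

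**The concern.** Evaluator blinding protects the measurement of outcomes. It does not conceal the next assignment from the people who decide whether a patient enters. One arm wears a footwear device and the other attends clinic sessions, so patients and therapists know the treatment, and past assignments are visible at the only site. Under blocking, past assignments carry information about the next one.

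Foreknowledge could act through eligibility criteria that need judgement, such as whether a patient can comply with study procedures, whether knee pain is referred from back or hip, and whether the patient counts as active. It could also act through timing. If the arm is assigned at week -2 and the qualifying VAS is taken at week 0, a patient could be kept or dropped on a subjective score after the arm is known.

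The primary outcomes, WOMAC pain and function at one year, are patient-reported, so selection on motivation or expectation would feed directly into the comparison. Section 5 plans ANOVA or a Kruskal-Wallis test and states no baseline adjustment. Adjustment could in any case deal only with measured factors.

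**Working it through.** The plan gives no predictability figure to reproduce, so the check has two parts: how much blocking could reveal, and what order the schedule implies.

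**Inputs**
- Ratio 1:2, physical therapy (P) to AposTherapy (A): section 4.3.
- Recruitment target 162, split 54:108: section 4.6.
- Block size: not stated. Assumed fixed at 3, 6, 9 or 12, since a 1:2 block must be a multiple of 3.
- Also assumed: staff know or infer the size and where each block starts, and they know past assignments.

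**Share determined by earlier assignments.** An assignment is certain once one arm is used up within its block. For a block with c P's and a A's, the expected number of certain assignments is a/(c+1) + c/(a+1): the A's expected after the last P, plus the P's expected after the last A. Dividing by c + a gives the share.

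- Size 3: 2/2 + 1/3 = 1.333; 1.333/3 = 44.4%
- Size 6: 4/3 + 2/5 = 1.733; 1.733/6 = 28.9%
- Size 9: 6/4 + 3/7 = 1.929; 1.929/9 = 21.4%
- Size 12: 8/5 + 4/9 = 2.044; 2.044/12 = 17.0%

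Size 3 can be checked by listing the blocks: PAA has 2 certain positions, APA has 1 and AAP has 1, which is 4 of 9.

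**Best-guess accuracy.** At each step, guess the arm with more places left in the block and count a tie as one half. For size 3, PAA scores 2, APA 2.5 and AAP 2.5; 7/9 = 77.8%. The other sizes follow by the same enumeration. Without blocking, always guessing AposTherapy is right 2/3 = 66.7% of the time.

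| Assumed fixed block | Certain | Of 162 (approx.) | Best guess right | Gain over 66.7% |
|---|---|---|---|---|
| 3 | 44.4% | 72 | 77.8% | 11.1 points |
| 6 | 28.9% | 47 | 74.4% | 7.7 points |
| 9 | 21.4% | 35 | 72.8% | 6.1 points |
| 12 | 17.0% | 28 | 71.7% | 5.0 points |

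(162 is not a whole number of blocks of 12, so that count is only approximate.) If someone on the recruiting side could open the list itself, every assignment would be known whatever the block size.

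**Order of events.** Section 4.5 makes a VAS of at least 3 cm, measured at baseline, a condition of entry. The schedule marks randomisation at week -2 and the first VAS at week 0. Read together, the arm is assigned before a qualifying measurement has been taken.

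**The case against.** The strongest reply is that concealment is undescribed, not shown to be broken. Entering and maintaining randomisation information may mean only recording assignments that have already been issued. The plan does not say that the coordinator generates the sequence, consents patients or judges eligibility. Section 4.5 draws patients from several clinics and practices, and the Resources table lists two coordinators, so duties could be divided. This stands. A reader might infer that the coordinator knows upcoming assignments, and the text does not support that.

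A reader might also infer that blocking plus a record of past assignments is enough to deduce the next one. It is not: the size must also be fixed and known or inferred, with the block boundaries. The protocol does not print a size, which is good practice if deliberate. The percentages above are therefore conditional. Even the largest gain in guessing accuracy is about 11 points, because 1:2 allocation is already fairly guessable.

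The Resources table lists "Full-time Apos resource to manage program on-site at Montefiore". A reader might see in this a route for the device provider to influence enrolment. No section gives that person a part in enrolment, eligibility or randomisation, so no weight is placed on it.

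On the schedule, eligibility is also marked at screening, so a qualifying VAS might be taken then without its own mark. That is possible, but the criterion says baseline and the only VAS marks start at week 0.

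What remains is that the sole custody arrangement stated is on site, no safeguard is stated anywhere, and the visit order as written lets the assignment precede confirmed eligibility.

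**Conclusion.** The point holds as a weakness in the stated arrangement, not as evidence that allocation was or will be subverted. Section 4.3 puts the randomisation information with on-site staff at a single, evaluator-blinded centre with blocked allocation, and nothing in the plan keeps upcoming assignments from those who recruit. The conditional size is 17% to 44% of assignments determined by earlier ones (about 28 to 72 of 162). It rests on assumed fixed blocks of 3 to 12 with the size and block starts known or inferred. With block sizes that vary and are unknown to the site, these figures would not apply.

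The order in the schedule is the firmer documentary support, because it needs no assumption about block size. It does depend on the week-0 VAS being the qualifying one.

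The resulting bias in WOMAC pain or function cannot be sized from the documents. It would be too strong to say that analysis can do nothing about it: imbalance in measured baseline factors can be partly adjusted for, but selection on unmeasured factors cannot.

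**What to change.** This is a cheap improvement. In section 4.3:

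- Have the biostatistician (100 hours are already in the Resources budget) or a computer randomisation module generate and hold the sequence, independent of recruitment.
- Use randomly varying block sizes, documented only outside the site protocol.
- Release one assignment at a time, only after consent, eligibility including baseline VAS, and baseline WOMAC have been recorded and locked.
- Limit the coordinator to recording the assignment once issued.

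In the study schedule, move the randomisation mark to after the baseline measures, so that it agrees with the inclusion criterion in section 4.5.

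The cost is a few hours of set-up, a shift of randomisation from screening to the baseline visit, and slightly more possible imbalance between arms at the end of recruitment. Neither the sample size nor the treatments change. If an independent holder and a release rule already exist, stating them in section 4.3 would settle that part, but the schedule would still need correcting.
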